8.7 Relevant Medical History

Relevant medical history will be self-reported and documented at SCR and will focus particularly on any important diseases and in case of infections or tumors, the pathogen involved or the pathological diagnosis, if available. In particular, subjects with prior COVID-19 infection need to include the infection and dates in the medical history section of the eCRF. Additionally, laboratory reports need to be documented during SCR. All ongoing conditions for which the subjects are taking medications, and/or which may exacerbate during the trial period should be considered as important. Special attention should be given to history of prior allergic reactions, especially to vaccines.

8.8 Prior and Concomitant Medication

All concomitant (ongoing) medication except homeopathic substances and dietary supplements must be recorded in the subject's medical record and in the eCRF including information about the indication, dosage regimen, and the onset and end of treatment.

The following medications taken within 3 months prior to SCR will also be recorded in the eCRF and the subjects medical record: vaccines (e.g., influenza/pneumococcal), corticosteroids (via any route of administration), other immune-modulating drugs, immunoglobulin and/or any blood products, investigational drugs and depot preparations which are still active at the date of SCR. In addition, subjects with previous SARS-CoV-2 vaccination will include the specific vaccine received by dose and date in the eCRF, regardless of the time elapsed prior to SCR.

8.9 Prohibited Medications

Prohibited medication or medication where washout periods need to be adhered to are (see also eligibility criteria in [Section 1.3](#)):

- Vaccination with any licensed live vaccine within 30 days prior to first or after last trial vaccination or any licensed inactivated vaccine within 14 days prior to first or after last trial vaccination.
- Start of chronic systemic administration (defined as more than 14 days of > 5 mg prednisone [or equivalent]) per day or any other systemic use of immune-modifying drugs during a period starting from 3 months prior to first administration of the trial vaccine and ending at the last visit of the active trial phase. The use of topical, inhaled, ophthalmic and nasal corticoids will be permitted.
- Administration of immunoglobulins and/or any blood products during a period starting from 3 months prior to first administration of the trial vaccine and ending at the last visit of the active trial phase.
- Use of any investigational or non-registered drug or vaccine other than the trial vaccine within 30 days preceding the administration of the trial vaccine, or planned administration of such a drug during the trial period until the FU Visit 3 months after the last vaccination visit for Group 1, or 24 months after last vaccination visit for Groups 2 and 3.
- In case official guidelines require booster vaccinations to maintain valid COVID-19 vaccination certificates, approved booster vaccinations for SARS-CoV-2 are allowed for Groups 2 and 3 within the follow-up period, however subjects will be withdrawn from further follow up.

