4.7 Early Discontinuation

Reasons for early discontinuations:

A subject may be discontinued from the trial early for different reasons. The decision to discontinue early can be made by the investigator or by the subject. Reasons for early discontinuation of a subject may include, but are not limited to:

- An AE/SAE/AESI that, in the opinion of the investigator, makes it unsafe for the subject to receive a vaccination
- Pregnancy
- An anaphylactic reaction following the administration of any vaccine(s)
- Clinical need for concomitant or ancillary therapy not permitted in the trial as outlined in [Section 8.8](#).
- Subject's receipt of an approved booster vaccination for SARS-CoV-2.
- Subject's request to discontinue (withdrawal of consent to participate).
- Subject unwilling or unable to comply with trial requirements.
- Any reason that, in the opinion of the investigator, requires or supports early discontinuation of a subject.

Handling of early discontinuations:

Each subject has the right to terminate their trial participation completely at any time for any reason, and the investigator may also terminate a subject's trial participation. Subjects whose trial participation is terminated during the active trial phase should undergo a concluding EAP visit, including safety laboratory testing and pregnancy test for WOCBP. The subject has the right to refuse the optional EAP visit, however, the CTS should make an effort to collect any safety data possible for the subject. If the subject consents, the 3-month FU visit (FU1) should still be performed to collect any potential SAEs/AESIs which occurred after the last vaccination. Subjects who discontinued after receiving trial vaccine will not be replaced.

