
Exploratory
 
 To assess SARS-CoV-2 specific peak humoral immune responses after the prime-boost regimen (Group 1) or the booster dose (Group 2 and Group 3) of the ABNCoV2 vaccine. To explore SARS-CoV-2 specific cellular immune responses to the ABNCoV2 vaccine. To assess SARS-CoV-2 specific neutralizing immune responses against variant strains circulating at the time of analysis. 	
 a) SARS-CoV-2 neutralizing antibody titers at 2 and 4 weeks post-prime vaccination and 1, 4, and 13 weeks post-boost vaccination (Group 1), and 1 week, 4 weeks, 3 months, 6 months, 1 year and 2 years after vaccination (Groups 2 and 3). b) Frequency and percentage of subjects in Groups 2 and 3 with SARS-CoV-2 neutralizing antibody titers having an at least 2-fold increase and 4-fold increase, respectively, from baseline at each sampling time point. c) SARS-CoV-2 total antibody titers (by ELISA) at all sampling time points. Cellular immune response, by Interferon-γ / Interleukin-4 ELISPOT, at 1 week after the last vaccination for all subjects. SARS-CoV-2 neutralizing antibody titers against variant strains circulating at the time of analysis at 2 weeks after last vaccination for all subjects.

Primary Estimand

The primary clinical question of interest is: What peak SARS-CoV-2 neutralizing antibodies titers can be achieved in seronegative (Group 1) and seropositive (Groups 2 and 3) adult subjects after protocol-specified vaccination regimen with ABNCoV2?

Treatment Condition: open-label, non-randomized treatment where subjects follow the protocol requirements and have no deviations from the protocol which would affect their SARS-CoV-2 neutralizing antibody titer levels at two weeks post the last vaccination with ABNCoV2.

Population: Seronegative (Group 1) or seropositive (Groups 2 and 3) adult subjects who meet all of the inclusion and none of the exclusion criteria for the trial, have their 2 weeks post-last vaccination neutralizing antibody titer result, and have no protocol violations which would affect the immunogenicity assessment for the trial.

Endpoint: SARS-CoV-2 neutralizing antibody titer at 2 weeks post-last vaccination (second vaccination for Group 1, and single boost vaccination for Groups 2 and 3).

Intercurrent Events:

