2.1 Multiplicity Adjustment

As no formal hypothesis testing will be performed, no adjustments for multiplicity will be needed.

3 Analysis Sets

The target analysis population for the trial includes subjects who meet all of the inclusion and none of the exclusion criteria as defined separately for each group (see Protocol Section 1.3). Subjects in Group 1 will be confirmed to be seronegative, and subjects in Groups 2 and 3 will be confirmed to be seropositive, and be stratified for enrollment by reason for seropositivity such that at least 40 subjects over both groups are enrolled for each of the three reasons for seropositivity (prior COVID-19 infection, prior mRNA vaccination, prior Adenovirus-based vaccination).

For the purposes of analysis, the following analysis sets are defined in [Table 1](#).

Table 1 Analysis Set Definitions

Participant Analysis Set	Description
Safety Analysis Set	All subjects who received at least 1 dose of ABNCoV2 vaccine. Subjects who are vaccinated are included in this set regardless of protocol violations or SARS-CoV-2 infection during the trial.
Immunogenicity Analysis Set	All subjects who are in the Safety Analysis Set and have at least 1 post-vaccination neutralizing antibody titer result. Subjects with protocol violations substantially affecting the immunogenicity outcomes will be excluded from this analysis set. For the purpose of the primary estimand, this includes SARS-CoV-2 infection prior to 2 weeks post last vaccination.

Protocol violations which may exclude a subject from the Immunogenicity Analysis Set may include, but are not limited to:

1. For Group 1, discontinuation prior to receiving both vaccinations
2. Enrollment into the incorrect SARS-CoV-2 exposure group, i.e., a seropositive subject enrolled into Group 1 or a seronegative subject enrolled into Group 2 or 3.
3. Major violation of the visit window affecting the immunogenicity results (i.e., the 2 weeks post-last vaccination serum sample is out of window).
4. Prohibited medication or vaccination given too close to the date of vaccination, or prior to collection of immunogenicity sample for the primary estimand time point, that may affect the immunogenicity results.
5. Major immunogenicity sample handling deviations at critical visits, e.g. regarding clotting time, turnaround time.
6. SARS-CoV-2 symptoms or infection prior to collection of the 2-week post-last vaccination immunogenicity sample.

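### Group 1: no rule sets aside a titer drawn after a non-trial SARS-CoV-2 vaccine, so the exploratory Week 17 GMT can carry another product's effect (minor)

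*Protocol*

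**What the plan says.** **Withdrawal and prohibited vaccines.** The last bullet of Protocol Section 8.9 says that approved boosters needed to keep a vaccination certificate valid "are allowed for Groups 2 and 3 within the follow-up period, however subjects will be withdrawn from further follow up". Group 1 is not mentioned there. The first bullet applies to every group: it bars licensed live vaccines for 30 days, and "any licensed inactivated vaccine within 14 days prior to first or after last trial vaccination". The bar that runs to the 3-month visit in Group 1 covers only investigational or non-registered products.

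**Discontinuation.** Protocol Section 4.7 opens its list with "Reasons for early discontinuation of a subject may include, but are not limited to", and one item is the subject's "receipt of an approved booster vaccination for SARS-CoV-2". The list is permissive and has no group limit.

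**Recording.** Protocol Section 8.8 requires that "subjects with previous SARS-CoV-2 vaccination will include the specific vaccine received by dose and date in the eCRF". A SARS-CoV-2 vaccine given later falls under general concomitant medication.

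**Analysis sets.** SAP Section 3, Table 1: "Subjects with protocol violations substantially affecting the immunogenicity outcomes will be excluded from this analysis set". Item 4 of the list below it reaches another vaccination given too near to trial dosing, or "prior to collection of immunogenicity sample for the primary estimand time point", which is Week 6 in Group 1. The list is open-ended, but every item removes a subject, not a sample.

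**Summaries.** SAP 4.2.4 presents titers by the visit of collection, without windowing, for both the Immunogenicity and the Safety Analysis Sets. SAP 4.4 uses whatever data are available in the Immunogenicity Analysis Set. Neither mentions samples drawn after another SARS-CoV-2 vaccine.

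**The concern.** In Groups 2 and 3, follow-up ends once another SARS-CoV-2 vaccine has been given, so later titers do not mix two products. Group 1 lacks that protection. Its subjects enter with no SARS-CoV-2 vaccine (exclusion criterion 1), and Protocol Section 2.5 itself expects much of the population to obtain an initial regimen within months. A licensed vaccination between the second trial dose and FU1 is therefore plausible, although no document says how frequent it would be.

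What is at stake is one descriptive result: the persistence of neutralizing and total antibody about 3 months after the two-dose regimen. If some of those titers come from another product, the Week 17 GMT would be read as ABNCoV2 durability when part of it is not.

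**Working it through.** **Inputs from the documents.** Group 1 n = 30, SD 0.5 on the log10 scale, two-sided 95% interval (Protocol 9.2, SAP Section 6). Sample windows in days after the second dose: Week 6 at 12–16, Week 8 at 28–35, Week 17 at 91–105 (Protocol 1.4).

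**Assumed inputs.** k = number of the 30 subjects vaccinated elsewhere before the sample; F = fold by which that vaccine raises their titer at the sample. The documents give neither. The SD of 0.5 was set for peak titers and is assumed to hold at Week 17.

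**1. The plan's own precision.** Half-width = 1.96 × 0.5/√30 = 0.179 log10, as stated. For a GMT of 200 this gives 132 to 302, also as stated. On the ratio scale, 10^0.179 = 1.51.

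**2. Is there time for another vaccine?** Day 15 is the first day outside the 14-day limit. From there to the Week 17 sample is 91 − 15 = 76 to 105 − 15 = 90 days. Counting from day 31, outside the 30-day limit, it is 60 to 74 days. The protocol does not class mRNA or vector vaccines as live or inactivated, but the window is long under either limit.

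**3. Inflation of the Week 17 GMT.** The log10 mean shifts by b = (k/30) × log10(F), so the GMT is multiplied by F^(k/30).

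| k of 30 | F = 2 | F = 4 | F = 10 |
|---|---|---|---|
| 3 | 1.07 | 1.15 | 1.26 |
| 6 | 1.15 | 1.32 | 1.58 |

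A shift as large as the half-width needs k = 30 × 0.179/log10(F), which is about 18 subjects at F = 2 and 6 at F = 10 (5.4, rounded up).

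**4. Coverage of the nominal 95% interval for the uncontaminated GMT.** Keeping the affected samples widens the spread: SD′ = √(0.25 + (30/29) × p(1 − p) × log10(F)²), with p = k/30 and h = 1.96 × SD′/√30. Coverage = Φ((h − b)/0.0913) − Φ((−h − b)/0.0913), where 0.0913 = 0.5/√30. For F = 2, 4, 10 this gives 94%, 92%, 89% at k = 3 and 91%, 81%, 63% at k = 6.

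**5. Precision with and without the affected samples (k = 6).** Dropping them leaves 24: 1.96 × 0.5/√24 = 0.200. Keeping them gives h = 0.184, 0.199, 0.231 for F = 2, 4, 10, around a biased estimate.

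**6. Week 8.** The Week 8 sample follows the Week 6 sample by 28 − 16 = 12 to 35 − 12 = 23 days (midpoint 17.5). Week 17 follows it by 91 − 16 = 75 to 105 − 12 = 93 days (midpoint 84). With even uptake, k = 6 at Week 17 means 6 × 17.5/84 = 1.25, about one subject, at Week 8. The factor is then F^(1/30) = 1.02, 1.05, 1.08.

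**7. Response rate including follow-up.** Suppose 27 of 30 respond to ABNCoV2 and a share u of the other 3 are vaccinated elsewhere and convert. The rate is (27 + 3u)/30, or 91% to 93% for u of 10% to 30%, instead of 90%.

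**The case against.** The strongest reply is that the booster bullet stands in a list of prohibited medications and makes an exception for Groups 2 and 3 only. By implication a licensed SARS-CoV-2 vaccine is not allowed in Group 1, so its receipt would be a deviation. The investigator could then discontinue the subject under Section 4.7, and the data review meeting could act. That reading is fair, but it does not close the gap. The stated action is removal of the whole subject from the Immunogenicity Analysis Set, which discards a valid Week 6 primary titer. The Week 17 titer would still appear in the Safety Analysis Set by-visit summary. If receipt is not a deviation, the Week 17 titer stays in both sets.

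Second, the information is not hidden. Concomitant medication is recorded and listed by subject, Group 1 is reported only at the final analysis (SAP 4.6 and 4.7), and SAP Section 1 allows documented additional analyses. This stands, and it lowers the severity. It leaves the handling to be decided after the titers may be known.

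Third, infection after Week 6 can also raise Week 17 titers, and the SAP only tabulates infections (4.5.3.4). This also stands: a vaccine rule alone does not make Week 17 a pure ABNCoV2 reading.

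A reader might infer that the missing compulsory withdrawal in Group 1 is itself the defect. The documents do not support that. Withdrawal would cost safety follow-up to FU1, and the bias comes from how samples are analysed. A reader might also infer that Week 8 or the response rates are distorted. Week 8 falls within the active phase, where the booster bullet gives no group permission, and steps 6 and 7 show negligible effects.

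**Conclusion.** The point holds for the Group 1 Week 17 summaries and is minor. Followed as written, the plan lets titers raised by a non-trial SARS-CoV-2 vaccine count as ABNCoV2 persistence, and its only exclusion tool is too blunt to correct this without losing primary data.

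The size rests wholly on assumed uptake and fold-rise. With 10% uptake the inflation is 1.07 to 1.26 and coverage stays near 90% or above. Only about 20% uptake with a large rise brings the bias to the scale of the planned interval. With no uptake there is no bias.

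It should not be read as a threat to the primary result. The Week 6 sample is drawn at day 12–16, is largely covered by the washout limits, and is covered by the SAP's exclusion of vaccination before the primary sample. No hypothesis is tested on any affected output.

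**What to change.** Add to SAP 4.2.4 and 4.4:

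*Immunogenicity results from samples drawn after a non-trial SARS-CoV-2 vaccine are excluded from the by-visit summaries; earlier results from the same subject, including the primary time point, are kept; the number excluded is shown by visit and group, and the summaries are repeated with all available data.*

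In Protocol Section 8.8 or 8.9, state that the product and date of any such vaccine in Group 1 are recorded through FU1.

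The cost is one SAP sentence and one protocol line, with no new visit, sample or test. Because Group 1 is reported at the final analysis, the rule can be fixed before its results are produced. The statistical cost is somewhat fewer Week 17 samples: with 24 instead of 30, the half-width is 0.200 instead of 0.179 log10. Every valid Week 6 titer is kept, and the all-data repeat shows the effect of the exclusion.

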1.3 Protocol Synopsis

Title	An Open Label Phase 2 Trial to Evaluate the Safety, Tolerability and Immunogenicity of the ABNCoV2 Vaccine in SARS-CoV-2 Seronegative and Seropositive Adult Subjects
Protocol Number	ABNCoV2-01
Clinical Phase	Phase 2
Sponsor	Bavarian Nordic A/S [name] [name] Denmark
Trial Identifier	EudraCT # 2021-001393-31
Number of Sites and Countries	2 sites, Germany
Vaccination Dose and Schedule	Each subject will receive either 2 doses of 100 µg (Group 1), 1 dose of 100 µg (Group 2) or 1 dose of 50 µg (Group 3) ABNCoV2 vaccine. In the case of the two-dose regimen, vaccines are administered 4 weeks apart.
Route of Administration	ABNCoV2 vaccine is administered intramuscularly (IM) into the deltoid muscle of the upper arm (preferably the non-dominant arm).
Trial Duration	Approximately 17 weeks for initially seronegative subjects receiving the two-dose vaccination regimen (Group 1). Up to 104 weeks for initially seropositive subjects receiving 1 vaccination (Group 2 and Group 3).
Sample Size	A total of 210 healthy adult subjects will be enrolled into 3 groups: 
 • Approx. 30 subjects determined to be seronegative for SARS-CoV-2 antibodies at screening (SCR) will be enrolled in Group 1. • Approx. 90 subjects determined to be seropositive for SARS-CoV-2 antibodies at SCR will be enrolled in Group 2 (100 µg). • Approx. 90 subjects determined to be seropositive for SARS-CoV-2 antibodies at SCR will be enrolled in Group 3 (50 µg).

Primary Objectives	To assess SARS-CoV-2 specific humoral immune responses of the ABNCoV2 vaccine in initially SARS-CoV-2 seronegative and seropositive subjects.
Secondary Objectives	To assess the safety and tolerability of the ABNCoV2 vaccine in adult seropositive and seronegative subjects.
Exploratory Objectives	
To assess SARS-CoV-2 specific peak humoral immune responses after the prime-boost regimen (Group 1) or the booster dose (Group 2 and Group 3) of the ABNCoV2 vaccine.
 
To explore SARS-CoV-2 specific cellular immune responses to the ABNCoV2 vaccine.
 
To assess SARS-CoV-2 specific neutralizing immune responses against variant strains circulating at the time of analysis.

Primary Endpoints	SARS-CoV-2 neutralizing antibody titers at 2 weeks after the last vaccination, i.e., after the second vaccination in initially seronegative subjects and after the single boost vaccination in initially seropositive subjects.

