4.5 Follow-Up Phase

To monitor long-term safety and immunogenicity, all subjects in Groups 1, 2 and 3 will come to the CTS for follow-up visits (FU1) 3 months after the last vaccination.

For additional immunogenicity and safety readouts, the Group 2 and Group 3 (initially seropositive) subjects, will come to the CTS for FU visits at 3 months (FU1), 6 months (FU2), 1 year (FU3) and 2 years (FU4) after their vaccination.

The procedures performed at the FU Visits are listed in the trial procedure schedule in [Section 1.4](#)

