8.12 Unsolicited AEs

All intercurrent diseases reported when the investigator actively inquires the subject will be documented and all required details (e.g., start and stop date, intensity) will be assessed. Unsolicited AEs will be reported in the subject's medical record and respective section of the eCRF (requirements for screen failures see [Section 12.1](#)).

Unsolicited AEs will be assessed and documented from ICF signature through EAP, and if ongoing at that time followed until resolution or until the subject's last trial visit, at the latest. SAEs and AESIs will be collected through the end of the trial, including during the FU period.

SAEs and AESIs will be assessed and documented at all trial visits. (S)AEs would only be considered as AESIs once subject has received first vaccination. SAEs and AESIs will be followed-up until resolution or achievement of stable clinical conditions.

Assessment of Intensity

For all unsolicited AEs not represented in the Toxicity Grading Scale for Healthy Adult and Adolescent Volunteers Enrolled in Preventive Vaccine Clinical Trials ([FDA, 2007](#)), the maximum intensity will be based on the following descriptions:

- Grade 1** An AE which is easily tolerated by the subject, causing minimal discomfort and not interfering with daily activities.
- Grade 2** An AE which is sufficiently discomforting to interfere with daily activities, but does not require medical intervention (non-narcotic pain reliever or other nonprescription medication are not considered “medical intervention” for this purpose).
- Grade 3** An AE which prevents daily activities and which requires medical intervention (non-narcotic pain reliever or other nonprescription medication are not considered “medical intervention” for this purpose)
- Grade 4** Life-threatening, or disabling.

Assessment of Causality

The relationship between the occurrence of an AE and the IMP will be assessed using the categories presented below. For expedited reporting and all other purposes, the categories “none” and “unlikely” will represent no evidence or argument to suggest a causal relationship, while “possible”, “probable” and “definite” will be seen to convey that there is evidence or argument to suggest a causal relationship. To ensure reporting, all AEs without a causality assessment from the investigator will preliminarily be classified as “possible”.

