4.2.4 Supplementary Analyses

The primary analysis will be supported by descriptive summaries including medians, geometric means and corresponding 95% CIs, Min, and Max for each serum collection time point. These summaries will be performed for both the Immunogenicity Analysis Set and the Safety Analysis Set. No windowing or imputation will be applied for this summary, as they will be presented by the visit at which the serum sample was acquired.

A responder analysis will be performed, with response analyzed by serum collection time point. Response defined separately for naïve subjects (Group 1) and experienced subjects (Groups 2 and 3) as follows:

- Group 1: having SARS-CoV-2 neutralizing antibody titers above the LLOQ, or
- Groups 2 and 3: having an at least 2-fold, 4-fold, and/or 6-fold increase from baseline SARS-CoV-2 neutralizing antibodies.

For Group 1, subjects are required to have a negative qualitative SARS-CoV-2 test at screening to enter the trial. Despite this, there is a chance they have positive neutralizing titer at baseline. In this case, response would be defined as an at least 2-fold increase from baseline in neutralizing titer.

Response rates will be summarized for the Immunogenicity Analysis Set by time point as well as overall for the Active Trial Period, and corresponding 95% CIs will be calculated using the Clopper-Pearson method. The response rate analysis will also be repeated for the Safety Analysis Set with subjects missing a value for a time point, and not having achieved a response at a previous timepoint, counted as non-responders. For the final CSR, an over response rate will be calculated inclusive of the FU visits in addition to the Active Trial Period rates.

The primary analyses will also be performed within sex (male vs. female) and age groups as supportive analyses: 18 to < 50 years, 50 to < 65 years, 65 to < 75 years, and \geq 75 years. These summaries will be performed for the Immunogenicity Analysis Set only.

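### Withdrawing boosted Group 2 and 3 subjects from further follow-up cuts short the planned SAE/AESI collection to week 104 and leaves the late exploratory titers on a changing unboosted subset

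*Protocol*

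**What the plan says.** Protocol 8.9 permits approved boosters where official guidelines require them for a valid certificate. They are "allowed for Groups 2 and 3 within the follow-up period, however subjects will be withdrawn from further follow up". Protocol 4.7 lists, among possible reasons for early discontinuation, "Subject's receipt of an approved booster vaccination for SARS-CoV-2".

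Other sections plan for longer observation. Protocol 8.12 states: "SAEs and AESIs will be collected through the end of the trial, including during the FU period". Protocol 4.5 opens with "To monitor long-term safety and immunogenicity, all subjects in Groups 1, 2 and 3 will come to the CTS". That sentence concerns the 3-month visit, but the next one extends safety and immunogenicity visits for Groups 2 and 3 to 2 years. The schedule marks SAE/AESI recording at FU1 to FU4, with FU4 at target week 104.

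The only contact provided for after discontinuation is in Protocol 4.7: "If the subject consents, the 3-month FU visit (FU1) should still be performed to collect any potential SAEs/AESIs which occurred after the last vaccination". It follows text about subjects who leave during the active phase.

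Late titers at 3 months, 6 months, 1 year and 2 years are exploratory endpoints (Protocol 1.3). SAP 4.4 analyses them on whatever data are available. SAP 4.2.4 applies no windowing or imputation to the time-point summaries: "they will be presented by the visit at which the serum sample was acquired". It also adds an overall response rate that includes the follow-up visits.

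**The concern.** The single trial dose in Groups 2 and 3 is given at V1, before any booster taken in follow-up. A booster makes later titers hard to attribute to ABNCoV2, which is a good reason to stop using them. It is not a reason to stop asking about SAEs and AESIs at visits already planned. The two purposes of follow-up are tied to one rule, and safety collection ends with the titers.

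For the titers, each late GMT describes those still unboosted and attending, while the week-2 GMT describes nearly everyone. SAP 4.4 plots these values over time. A plateau or decline on that plot could reflect who remains rather than how the response lasts. A post-booster sample, if one were drawn and used, would enter the by-visit GMT, the fold increase and the response rates, because nothing in the SAP removes it.

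**Working it through.** **1. Passages side by side**

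- Collection runs to the end of the trial (8.12; schedule through FU4), yet a boosted subject leaves further follow-up (8.9).
- 4.7 makes any approved booster a possible reason for discontinuation; 8.9 makes withdrawal automatic for boosters in follow-up.
- FU1 may survive with consent under 4.7. Whether that covers a booster taken between the week-4 visit and FU1 is unclear. Nothing covers FU2 to FU4.
- Booster receipt is not among the intercurrent events (Protocol 9.9; SAP 1.1). The exclusion for other vaccinations in SAP section 3 (item 4) concerns those near the trial dose or before the primary sample. The exclusion list is settled before the primary analysis, which SAP 4.6 triggers once Groups 2 and 3 complete the end-of-active-phase visit.

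**2. The plan's own precision** (Protocol 9.2; SAP section 6). Inputs: log10 SD 0.5, pre/post correlation 0.3, n = 90.

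- SD of the log10 difference = √(2 × 0.5² × (1 − 0.3)) = 0.5916.
- Half-width = 1.96 × 0.5916 / √90 = 0.122. Around a 4-fold rise: 4 × 10^(±0.122) = 3.0 to 5.3.
- With n = 45: half-width 0.173, lower bound 2.7.

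All three stated figures reproduce.

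**3. Illustration.** Let b be the share withdrawn after a booster by 2 years. The documents do not give it, so 20% to 80% is an assumption.

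- Zero-event two-sided 95% Clopper-Pearson upper bound, both seropositive groups pooled: 1 − 0.025^(1/n), n = 180 × (1 − b).
- Late fold-increase interval per group: the step 2 formula with n = 90 × (1 − b), assuming the week-2 SD and correlation still apply.
- Possible shift in a late GMT under a normal selection model: 10^(r × 0.5 × φ(z_b)/(1 − b)). Here z_b is the standard normal quantile at b, φ is the normal density, and r is the correlation between remaining unboosted and log10 titer. r = 0.3 is assumed.

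| b | Pooled n | Zero-event bound | n per group | Half-width | Interval around 4-fold | GMT factor, r = 0.3 |
|---|---|---|---|---|---|---|
| 0 | 180 | 2.0% | 90 | 0.122 | 3.0–5.3 | none |
| 20% | 144 | 2.5% | 72 | 0.137 | 2.9–5.5 | 1.13 |
| 40% | 108 | 3.4% | 54 | 0.158 | 2.8–5.8 | 1.25 |
| 60% | 72 | 5.0% | 36 | 0.193 | 2.6–6.2 | 1.40 |
| 80% | 36 | 9.7% | 18 | 0.273 | 2.1–7.5 | 1.62 |

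Over the same values of b, the factor runs from 1.04 to 1.17 at r = 0.1 and from 1.22 to 2.24 at r = 0.5. If r is negative, the shift is the reciprocal.

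**4. Credit for time observed.** The bound treats a withdrawn subject as never followed. Counting person-time instead, 180 × 2 = 360 planned person-years become 180 × (2(1 − b) + 0.5b) if withdrawals fall at 6 months: 306, 252, 198 and 144 for b = 20%, 40%, 60% and 80%. If they fall at 1 year, the figures are 324, 288, 252 and 216. One subject boosted at week 26 loses (104 − 26)/104 = 75% of planned follow-up; at week 52, 50%.

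**The case against.** The rule was a deliberate addition in Amendment 2, and the participation time of up to 104 weeks allows for early exit. Events and titers after another SARS-CoV-2 vaccine are hard to attribute. The week-2 primary and 8-day secondary endpoints fall before the period in which the rule applies. All of that stands, and it limits the point to exploratory titers and follow-up safety listings.

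Several stronger readings are tempting, and the documents do not support them.

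- *A 2-year safety objective is lost.* The objective is "To assess the safety and tolerability of the ABNCoV2 vaccine in adult seropositive and seronegative subjects", with no time horizon. Its endpoints run 8 days, the further safety endpoints at most 29, and SAP 4.5.2.2 only lists follow-up events. What shrinks is planned collection.
- *All follow-up stops.* The wording is further follow-up. FU1 may remain, and 8.12 follows SAEs and AESIs that have already begun until they resolve or stabilise.
- *The remaining subjects are self-selected.* Permission is tied to official certificate requirements. Who takes a booster, and whether that relates to titer, is not stated.
- *Late titers will be contaminated.* Under 8.9 a boosted subject leaves, so later serum is not planned. Neither document says when sites learn of a booster. The missing exclusion rule is a gap, not a demonstrated distortion.
- *Boosters go unrecorded after FU1.* SAP Appendix 3 prints concomitant-medication marks only to FU1, but the protocol schedule prints them beyond it and Protocol 8.8 requires all concomitant medication to be recorded.

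**Conclusion.** The point holds at limited scope. Protocol 8.9 and 4.7 conflict in effect with 4.5, 8.12 and the schedule, and the result is an early end to planned SAE/AESI collection for a non-safety reason. The 6-month to 2-year titers describe a changing unboosted subset, with no same-subject comparison and no rule for samples taken after a non-trial vaccine. The direction of any titer bias is unknown.

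The size depends on uptake, which the documents do not give. Over the assumed range the loss runs from slight at 20% withdrawn to a nearly fivefold wider zero-event bound at 80% (9.7/2.0). That upper figure overstates the loss because it ignores months already observed, and it bounds a rate that neither document plans to estimate. The case for change rests on its low cost, not on any threat to the main results.

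**What to change.** **Protocol.** Reconcile 4.7, 8.9 and 8.12 so that booster receipt ends a subject's contribution to the titer summaries but not SAE/AESI collection at the follow-up visits already scheduled. Permission to take a booster stays as it is. Record booster product and date, and list SAEs and AESIs before and after the booster separately.

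**SAP.** In 4.2.4 and 4.4:

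- Exclude titers drawn after a non-trial SARS-CoV-2 vaccine from the by-visit GMT, GMFI and response summaries, including the overall response rate that covers follow-up visits.
- Report the number leaving the titer summaries for a booster, by visit and group.
- Beside each late GMT, show the week-2 GMT of the same contributing subjects.

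**Cost.** Protocol and SAP wording, plus attendance by boosted subjects at visits already in the schedule. SAEs after a booster remain confounded by it; the before/after listing makes that visible but does not remove it.
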